12.4.1. Definition of Adverse Events

Adverse Event Definition:

- An AE is any untoward medical occurrence in a patient or clinical investigation subject, temporally associated with the use of a medicinal product, whether or not considered related to the medicinal product.
- NOTE: An AE can therefore be any unfavorable and unintended sign (including an abnormal laboratory finding), symptom, or disease (new or exacerbated) temporally associated with the use of a medicinal product.

Events meeting AE definition include:

- Any abnormal laboratory test results (hematology, clinical chemistry, or urinalysis) or other safety assessments (e.g., ECGs, radiological scans, vital signs measurements), including those that worsen from baseline, and felt to be clinically significant in the medical and scientific judgement of the investigator.
- Exacerbation of a chronic or intermittent pre-existing condition including either an increase in frequency and/or intensity of the condition.
- New conditions detected or diagnosed after study treatment administration even though it may have been present prior to the start of the study.
- Signs, symptoms, or the clinical sequelae of a suspected interaction.
- Signs, symptoms, or the clinical sequelae of a suspected overdose of either study treatment or a concomitant medication (overdose per se will not be reported as an AE/SAE unless this is an intentional overdose taken with possible suicidal/self-harming intent. This should be reported regardless of sequelae).
- "Lack of efficacy" or "failure of expected pharmacological action" per se will not be reported as an AE or SAE. However, the signs and symptoms and/or clinical sequelae resulting from lack of efficacy will be reported if they fulfil the definition of an AE or SAE.
- The signs and symptoms and/or clinical sequelae resulting from lack of efficacy will be reported if they fulfil the definition of an AE or SAE. Also, "lack of efficacy" or "failure of expected pharmacological action" also constitutes an AE or SAE.

Events NOT meeting definition of an AE include:

- Any clinically significant abnormal laboratory findings or other abnormal safety assessments which are associated with the underlying disease, unless judged by the investigator to be more severe than expected for the subject's condition.
- The disease/disorder being studied or expected progression, signs, or symptoms of the disease/disorder being studied, unless more severe than expected for the subject's condition.
- Medical or surgical procedure (e.g., endoscopy, appendectomy): the condition that leads to the procedure is an AE.
- Situations where an untoward medical occurrence did not occur (social and/or convenience admission to a hospital).
- Anticipated day-to-day fluctuations of pre-existing disease(s) or condition(s) present or detected at the start of the study that do not worsen.

12.4.2. Definition of Serious Adverse Events

If an event is not an AE per definition above, then it cannot be an SAE even if serious conditions are met (e.g., hospitalization for signs/symptoms of the disease under study, death due to progression of disease, etc).

Serious Adverse Event (SAE) is defined as any untoward medical occurrence that, at any dose:**a. Results in death****b. Is life-threatening****NOTE:**

The term 'life-threatening' in the definition of 'serious' refers to an event in which the subject was at risk of death at the time of the event. It does not refer to an event, which hypothetically might have caused death, if it were more severe.

c. Requires hospitalization or prolongation of existing hospitalization**NOTE:**

- In general, hospitalization signifies that the subject has been detained (usually involving at least an overnight stay) at the hospital or emergency ward for observation and/or treatment that would not have been appropriate in the physician's office or out-patient setting. Complications that occur during hospitalization are AEs. If a complication prolongs hospitalization or fulfills any other serious criteria, the event is serious. When in doubt as to whether "hospitalization" occurred or was necessary, the AE should be considered serious.
- Hospitalization for elective treatment of a pre-existing condition that did not worsen

Serious Adverse Event (SAE) is defined as any untoward medical occurrence that, at any dose:

from baseline is not considered an AE.

d. Results in disability/incapacity

NOTE:

- The term disability means a substantial disruption of a person's ability to conduct normal life functions.
- This definition is not intended to include experiences of relatively minor medical significance such as uncomplicated headache, nausea, vomiting, diarrhea, influenza, and accidental trauma (e.g. sprained ankle) which may interfere or prevent everyday life functions but do not constitute a substantial disruption

e. Is a congenital anomaly/birth defect

f. Other situations:

- Medical or scientific judgment should be exercised in deciding whether reporting is appropriate in other situations, such as important medical events that may not be immediately life-threatening or result in death or hospitalization but may jeopardize the subject or may require medical or surgical intervention to prevent one of the other outcomes listed in the above definition. These should also be considered serious.
- Examples of such events are invasive or malignant cancers, intensive treatment in an emergency room or at home for allergic bronchospasm, blood dyscrasias or convulsions that do not result in hospitalization, or development of drug dependency or drug abuse

g. Is associated with liver injury and impaired liver function defined as:

- ALT \geq 3xULN and total bilirubin* \geq 2xULN (>35% direct), or
- ALT \geq 3xULN and INR ** > 1.5 .

* Serum bilirubin fractionation should be performed if testing is available; if unavailable, measure urinary bilirubin via dipstick. If fractionation is unavailable and ALT \geq 3xULN and total bilirubin \geq 2xULN, then the event is still to be reported as an SAE.

** INR testing not required per protocol and the threshold value does not apply to subjects receiving anticoagulants. If INR measurement is obtained, the value is to be recorded on the SAE form.

- Refer to [Appendix 2](#) for the required liver chemistry follow-up instructions

12.4.3. Definition of Cardiovascular Events

Cardiovascular Events (CV) Definition:

Investigators will be required to fill out the specific CV event page of the CRF for the following AEs and SAEs:

- Myocardial infarction/unstable angina
- Congestive heart failure
- Arrhythmias
- Valvulopathy
- Pulmonary hypertension
- Cerebrovascular events/stroke and transient ischemic attack
- Peripheral arterial thromboembolism
- Deep venous thrombosis/pulmonary embolism
- Revascularization

12.4.4. Recording of AEs and SAEs

AEs and SAE Recording:

- When an AE/SAE occurs, it is the responsibility of the investigator to review all documentation (e.g., hospital progress notes, laboratory, and diagnostics reports) relative to the event.
- The investigator will then record all relevant information regarding an AE/SAE in the CRF
- It is **not** acceptable for the investigator to send photocopies of the subject's medical records to GSK in lieu of completion of the GSK, AE/SAE CRF page.
- There may be instances when copies of medical records for certain cases are requested by GSK. In this instance, all subject identifiers, with the exception of the subject number, will be blinded on the copies of the medical records prior to submission of to GSK.
- The investigator will attempt to establish a diagnosis of the event based on signs, symptoms, and/or other clinical information. In such cases, the diagnosis will be documented as the AE/SAE and not the individual signs/symptoms.
- Subject-completed Value Evidence and Outcomes questionnaires and the collection of AE data are independent components of the study.
- Responses to each question in the Value Evidence and Outcomes questionnaire will be treated in accordance with standard scoring and statistical procedures detailed by

AEs and SAE Recording:

the scale's developer.

- The use of a single question from a multidimensional health survey to designate a cause-effect relationship to an AE is inappropriate.

12.4.5. Evaluating AEs and SAEs**Assessment of Intensity**

The investigator will make an assessment of intensity for each AE and SAE reported during the study and will assign it to one of the following categories:

- Mild: An event that is easily tolerated by the subject, causing minimal discomfort and not interfering with everyday activities.
- Moderate: An event that is sufficiently discomforting to interfere with normal everyday activities
- Severe: An event that prevents normal everyday activities. - an AE that is assessed as severe will not be confused with an SAE. Severity is a category utilized for rating the intensity of an event; and both AEs and SAEs can be assessed as severe.
- An event is defined as 'serious' when it meets at least one of the pre-defined outcomes as described in the definition of an SAE.

Assessment of Causality

- The investigator is obligated to assess the relationship between study treatment and the occurrence of each AE/SAE.
- A "reasonable possibility" is meant to convey that there are facts/evidence or arguments to suggest a causal relationship, rather than a relationship cannot be ruled out.
- The investigator will use clinical judgment to determine the relationship.
- Alternative causes, such as natural history of the underlying diseases, concomitant therapy, other risk factors, and the temporal relationship of the event to the study treatment will be considered and investigated.
- The investigator will also consult the Investigator Brochure (IB) and/or Product Information, for marketed products, in the determination of his/her assessment.
- For each AE/SAE the investigator **must** document in the medical notes that he/she has reviewed the AE/SAE and has provided an assessment of causality.
- There may be situations when an SAE has occurred and the investigator has minimal information to include in the initial report to GSK. However, **it is very important**

Assessment of Causality

that the investigator always make an assessment of causality for every event prior to the initial transmission of the SAE data to GSK.

- The investigator may change his/her opinion of causality in light of follow-up information, amending the SAE data collection tool accordingly.
- The causality assessment is one of the criteria used when determining regulatory reporting requirements.

Follow-up of AEs and SAEs

- The investigator is obligated to perform or arrange for the conduct of supplemental measurements and/or evaluations as may be indicated or as requested by GSK to elucidate as fully as possible the nature and/or causality of the AE or SAE.
- The investigator is obligated to assist. This may include additional laboratory tests or investigations, histopathological examinations or consultation with other health care professionals.
- If a subject dies during participation in the study or during a recognized follow-up period, the investigator will provide GSK with a copy of any post-mortem findings, including histopathology.
- New or updated information will be recorded in the originally completed CRF.
- The investigator will submit any updated SAE data to GSK within the designated reporting time frames.

12.4.6. Reporting of SAEs to GSK**SAE reporting to GSK via electronic data collection tool**

- Primary mechanism for reporting SAEs to GSK will be the electronic data collection tool
- If the electronic system is unavailable for greater than 24 hours, the site will use the paper SAE data collection tool and fax it to the Medical Monitor.
- Site will enter the serious adverse event data into the electronic system as soon as it becomes available.
- After the study is completed at a given site, the electronic data collection tool (InForm system) will be taken off-line to prevent the entry of new data or changes to existing data
- If a site receives a report of a new SAE from a study subject or receives updated data on a previously reported SAE after the electronic data collection tool has been taken off-line, the site can report this information on a paper SAE form or to the Medical Monitor by telephone.

SAE reporting to GSK via electronic data collection tool

[figure not shown]
- Contacts for SAE receipt can be found at the beginning of this protocol on the Sponsor/Medical Monitor Contact Information page.

12.5. Appendix 5: Collection of Pregnancy Information

- Investigator will attempt to collect pregnancy information on any female partner of a male study subject who becomes pregnant while participating in this study. This applies only to subjects who are randomized to receive study medication.
- After obtaining the necessary signed informed consent from the female partner directly, the investigator will record pregnancy information on the appropriate form and submit it to GSK within 2 weeks of learning of the partner's pregnancy
- Partner will also be followed to determine the outcome of the pregnancy. Information on the status of the mother and child will be forwarded to GSK.
- Generally, follow-up will be no longer than 6 to 8 weeks following the estimated delivery date. Any termination of the pregnancy will be reported regardless of fetal status (presence or absence of anomalies) or indication for procedure.

[figure not shown]
12.6. Appendix 6: Dyspnea 5-Point Likert Scale

CCI - This section contained Clinical Outcome Assessment data collection questionnaires or indices, which are protected by third party copyright laws and therefore have been excluded.

12.7. **Appendix 7: Columbia Suicide-Severity Rating Scale (C-SSRS)**

CCI - This section contained Clinical Outcome Assessment data collection questionnaires or indices, which are protected by third party copyright laws and therefore have been excluded.

[figure not shown]

**COLUMBIA SUICIDE-SEVERITY
RATING SCALE (C-SSRS)**

CCI - This section contained Clinical Outcome Assessment data collection questionnaires or indices, which are protected by third party copyright laws and therefore have been excluded.

12.8. Appendix 8: SF-36 Acute

CCI - This section contained Clinical Outcome Assessment data collection questionnaires or indices, which are protected by third party copyright laws and therefore have been excluded.

12.9. Appendix 9: Intravenous Saline Infusion

Rapid intravenous saline infusion has been employed to elicit fluid extravasation from the vasculature to the pulmonary interstitium. This methodology has been previously utilized in studies with healthy volunteers [[Synder, 2006](#)] and patients with heart failure [[Fujimoto, 2013](#); [Robbins, 2014](#); [Andersen, 2015](#)].

Subject Evaluation Prior to Infusion

On Day 5 of both study periods, the subject will be admitted to the unit and undergo routine weight measurement and vital sign assessments including temperature, systolic and diastolic blood pressures, heart rate, respiratory rate, and pulse oximetry to assess O₂ saturation. The subject will also undergo a pulmonary examination.

While in a sitting position, a dyspnea assessment, utilizing a standardized 5-point Likert scale, will be obtained to document the subject's current status. A subject who is not severely or very severely short of breath will undergo an orthopnea test (placed supine with head \leq 20 degrees relative to horizontal). After an equilibration period of 2 minutes, the 5-point scale will be repeated. A subject who reports a worse dyspnea score when supine compared to sitting will be categorized as having orthopnea. Subjects categorized as having orthopnea will not be eligible to participate in the saline infusion.

Study treatment will be administered after all planned pre-dose assessments for Day 5 are completed.

Saline Infusion Procedure

A subject who is judged by the Investigator to be in a stable condition and without obvious congestion will then undergo the intravenous saline infusion procedure. This procedure will be conducted in the unit, in the presence of a cardiologist and monitoring personnel. A crash cart will be accessible, and intravenous diuretic will be available, if necessary.

A venous catheter will be inserted while the subject is semi-recumbent (approximately 45°). The subject will remain in a semi-recumbent position throughout the procedure.

DLco and DLno measurements and simple spirometry assessments will be obtained prior to the initiation of the infusion.

0.9% normal saline will be infused intravenously at a rate of approximately 150 mL/min to a total volume of 500 mL. During the saline infusion, blood pressure, heart rate, respiratory rate, and O₂ saturation will be continuously monitored, and any physical symptoms recorded.

DLco and DLno measurements and spirometry assessments will be obtained after the completion of the infusion. Additional details are provided in the SRM.

Post-infusion Monitoring

Following the completion of the saline infusion procedure, the subject will remain in the unit for the next 4 hours. Blood pressure, heart rate, respiratory rate, and O₂ saturation will be continuously monitored, and any physical symptoms recorded. The subject will also be assessed for dyspnea and orthopnea, as described above, at hourly intervals.

After the 4-hour period, the subject will be eligible to leave the unit if heart rate and respiratory rate are within 20% of the baseline value, O₂ saturation is within 2% of the baseline value, and if the dyspnea score is the same as the baseline score.

The subject will continue to be monitored by the Preventice BodyGuardian Remote Monitoring System as described in Section 7.4.7 of the protocol; ECG, heart rate, respiratory rate and activity level will be measured continuously.

Any worsening of heart failure that requires treatment in the 48 hours subsequent to the saline infusion will be reported as a serious adverse event.

Individual Stopping Criteria During the Saline Infusion Procedure

If the subject demonstrates one of the following changes during the saline infusion, the infusion should be discontinued:

- Decrease in O₂ saturation of >4% compared to baseline
- Increase in respiratory rate of >20% compared to baseline
- Any increase in dyspnea perceived by the patient

If the subject has met one of these criteria during or immediately after the infusion, the subject should be carefully monitored and given intravenous diuretic treatment, intravenous or sublingual nitrates, or other treatment as required.

The subject may continue in the study. However, if this response occurred in the first study period, the subject should not undergo a second saline infusion in the subsequent study period.

Discontinuation of Saline Infusion Procedure

If during the conduct of the study, two subjects meet the individual stopping criteria during the infusion or demonstrate a worsening of heart failure in the 48 hours after completion of the infusion, this challenge procedure will be removed from the study design. No other subjects will undergo this assessment.

Reporting of Adverse Outcomes Associated with the Saline Infusion

Any of the following outcomes must be reported to the sponsor as a serious adverse event:

- Treatment with intravenous diuretic subsequent to the saline infusion

- Need for continued monitoring in the unit beyond the 4-hour mandated observation period
- Any worsening of heart failure that requires treatment during the 48-hour monitoring period after the saline infusion procedure

These events will be reported by the investigator as serious adverse events in the InForm electronic data collection tool. They will be reported by the sponsor to the FDA as an Expedited Report via electronic submission in eCTD format to the IND, as a 7-day or 15-day IND safety report, as applicable per timeframe specified in 21 CFR 312.32(c)(1). The completed report will also be provided to the IRB.

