7.3.3. Intravenous Saline Infusion

In patients with chronic HF, intravenously infused saline elicited a reduction of D_M [Puri, 1999] suggesting that the abnormal pulmonary diffusion in this population may have a variable component that could be amenable to therapeutic intervention. Similarly, an infusion of saline into the pulmonary artery significantly reduced both DLco and D_M in patients with chronic HF but not in control subjects [Guazzi, 1999]; the changes in D_M were inversely related to VE/VCO₂ [Guazzi, 2001]. The hemodynamic effects of volume

expansion with saline loading has been shown to be associated with increases in left and right heart filling pressures and pulmonary artery pressures in patients with HF [Andersen, 2015]. In this latter study, no patient developed dyspnea or any evidence of pulmonary congestion despite increase in cardiac filling pressures.

All subjects will undergo an intravenous 0.9% NaCl infusion on Day 5 of both study periods in the presence of a cardiologist. The procedure will be conducted only if the subject is without any signs of obvious congestion as determined by the Investigator. Subjects will be carefully monitored both during and after the infusion and will be provided intravenous diuretics if necessary. Details of this procedure are described in [Appendix 9](#).

DLco and DLno measurements will be obtained prior to the initiation of the infusion and after the completion of the infusion. Additional details are included in the SRM.

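### Reactions just after the saline infusion bar a subject from re-infusion but do not by themselves count toward the two-subject rule that removes the challenge

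*Protocol*

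**What the plan says.** Protocol Section 7.3.3 plans the challenge for everyone: "All subjects will undergo an intravenous 0.9% NaCl infusion on Day 5 of both study periods". Appendix 9 (Section 12.9) sets the infusion "at a rate of approximately 150 mL/min to a total volume of 500 mL". It excludes subjects with orthopnea and requires the investigator to judge the subject stable and without obvious congestion.

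Under the individual stopping criteria, Appendix 9 lists three changes: O2 saturation down by more than 4%, respiratory rate up by more than 20%, and any perceived increase in dyspnea. If one occurs while the infusion is running, the infusion stops. Monitoring and treatment have a wider window: "If the subject has met one of these criteria during or immediately after the infusion". The bar on re-infusion follows from the same response: "if this response occurred in the first study period, the subject should not undergo a second saline infusion in the subsequent study period".

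The study-level rule, under the next subheading, removes the challenge for all later subjects if "two subjects meet the individual stopping criteria during the infusion or demonstrate a worsening of heart failure in the 48 hours after completion".

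On observation after the infusion: "Following the completion of the saline infusion procedure, the subject will remain in the unit for the next 4 hours". Over those hours respiratory rate and O2 saturation are monitored continuously. For dyspnea: "The subject will also be assessed for dyspnea and orthopnea, as described above, at hourly intervals".

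Three outcomes must be reported as serious adverse events. One is "Treatment with intravenous diuretic subsequent to the saline infusion". The others are a need for monitoring in the unit beyond the 4 hours, and worsening of heart failure that requires treatment within 48 hours. Protocol Section 9.3.2 adds in-stream review of safety data by the sponsor.

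**The concern.** The same three criteria are used for two purposes with two different windows. For the individual, a reaction just after the infusion has the same consequences as one during it: monitoring, treatment as required, and no second infusion. For the study, it does not count unless it is also worsening of heart failure. The protocol gives no reason for the difference.

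The removal rule exists to protect subjects not yet infused. The population is NYHA Class II-IV heart failure (Protocol Section 5.1), and the risk table in Section 4.6.1 names dyspnea and exacerbation of congestive heart failure as possible effects of the infusion. At stake is whether two objective reactions stop the challenge automatically, or whether stopping depends on what someone decides to call them.

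**Working it through.** There is no sample size, power or error rate to reproduce here. The check is one division and a comparison of the rules.

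**Length of the infusion.** Inputs: total volume 500 mL and rate about 150 mL/min, both from Appendix 9.

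- Duration = volume / rate = 500 / 150 = 3.33 min, or 200 s.
- In-unit observation afterwards = 4 h = 240 min.

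The criteria limb of the removal rule is therefore open for about 3.3 min. The 48-hour limb begins at completion, so the rule as a whole leaves no gap in time. What changes at completion is the kind of event that counts.

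**The rules side by side, as written in Appendix 9.**

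| Event | Individual consequence | Counts toward removal? |
|---|---|---|
| Criterion met during the infusion | Infusion stopped; monitored and treated as required; no second infusion if Period I | Yes, first limb |
| Criterion met immediately after, also called worsening of heart failure | Monitored and treated as required; no second infusion if Period I | Yes, second limb |
| Criterion met immediately after, not called worsening of heart failure | Monitored and treated as required; no second infusion if Period I | No |
| Worsening of heart failure later within 48 hours, no criterion met during or immediately after | Not named in the no-second-infusion sentence | Yes, second limb |

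The third row is the gap. The fourth row shows that the rules differ in both directions: the removal rule reaches further in time, the individual rule further in type of event.

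**Does other text close the third row?**

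- *Definition.* Appendix 9 does not define worsening of heart failure or link it to the three criteria. A respiratory rate rise above 20%, or a perceived increase in dyspnea, can meet a criterion without carrying that label.
- *SAE list.* Intravenous diuretic after the infusion and treated worsening of heart failure are separate items. The list requires reporting, including expedited reporting, but does not require removal.
- *Sponsor review.* Section 9.3.2 concerns review of data and the decision to continue or stop recruitment. It does not make an event count toward removal of the challenge.

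So, as written, two subjects can each react just after the infusion, each be barred from a second one if in Period I, and the challenge can continue.

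**The case against.** The best defence is that the difference is deliberate. The criteria are introduced to stop a running infusion; once it has finished there is nothing to stop, so the protocol moves to a clinical endpoint. The infusion is meant to push fluid into the pulmonary interstitium, and DLco, DLno and spirometry manoeuvres follow it. A brief rise in respiratory rate or some breathlessness may then be the intended physiology or the effect of testing. On this view it is reasonable to handle the individual cautiously without letting two such episodes end a secondary objective. A cardiologist is present, and the serious outcomes are reported to the sponsor, the FDA and the IRB.

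Part of this stands. The backstops are real, and the 48-hour limb should catch most clinically important reactions. The argument that nothing is left to stop does not carry over, because the removal rule acts on later subjects. The protocol also already treats a reaction just after the infusion like one during it when deciding whether that person may be infused again.

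Several stronger readings are tempting and are not supported:

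- *The safety stop works for only 3.3 minutes.* That describes one limb. The rule as a whole runs to 48 hours after completion.
- *The investigator alone decides whether a later reaction counts.* The removal rule names no judge. This is an inference from the undefined term and from the investigator's reporting role.
- *Many further infusions would go ahead after two reactions.* One can construct a worst case in which the first two subjects infused are the reactors and nothing later triggers the rule. With no reaction rate in the documents, that count does not measure the effect.
- *Late reactors are worse off because they have had the full volume.* Nothing in the documents links volume received to severity.
- *Every use of intravenous diuretic should count as worsening of heart failure.* Appendix 9 lists the two separately, and giving a diuretic is a treatment decision. Making it a removal trigger is a further and debatable step.

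**Conclusion.** The mismatch is real and the point is minor. A reaction immediately after the infusion is enough to bar a Period I subject from a second infusion, but it does not by itself count toward removing the challenge. After the first 3.3 minutes or so, removal depends on an undefined clinical term.

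This rests on a literal reading of Appendix 9 and on the nominal rate and volume. It does not rest on any assumed frequency of reactions; none is given, and no probability or number of affected subjects is claimed. The saline-challenge measurements are secondary, so the primary endpoint is not at issue.

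**What to change.** In the first limb of the removal rule, count the individual criteria when met during *or immediately after* the infusion. Leave the 48-hour limb as it is.

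*Immediately after* is itself undefined in Appendix 9, so copying it alone would carry the vagueness across. Give it one stated time window and use that window in both rules. The length is for the sponsor to choose. Respiratory rate and O2 saturation are already continuous over the 4 hours, but dyspnea is scheduled hourly. A window that ends at the first hourly dyspnea score would need no new assessment; a shorter one would need a dyspnea score at completion.

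The cost is a sentence or two in Appendix 9. The downside is that the challenge may be removed earlier, leaving fewer secondary saline DLco and DLno data. That is a small price for making the study-level rule consistent with the individual one.
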